## 2.AIM / OBJECTIVES

This study aims to assess the effect of Dienogest and NAC on the volume of uterine leiomyoma in women previously diagnosed with leiomyoma.

**Research hypothesis:** In women with leiomyoma, the use of NAC as a non-hormonal drug in the treatment of leiomyoma of the uterus is more feasible and effective in the reduction of leiomyoma volume with no hormonal side effects compared with Dienogest.

**Research question:** In women with leiomyoma, is the use of NAC as a non-hormonal drug in the treatment of leiomyoma of the uterus more feasible and effective in the reduction of leiomyoma volume with no hormonal side effects compared with Dienogest?

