### **Sample size Justification:**

Assuming an effect size of 1.0 reflecting the percentage change (reduction) in the volume of uterine leiomyoma, a sample of 12 patients in each group will be enough to detect such rate, if true, at 0.01  $\alpha$  error and 0.90 power of the test. We will increase the sample to 20 cases in each group to maximize the power of the study.

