### **Study procedures and interventions:**

1. After approval of study protocol, women will be enrolled into the study according to inclusion and exclusion criteria.
2. Eligible patients will be randomized using a computer-generated sequence 1:1 either to
3. **Intervention:**
  - Group (A): women will receive Dienogest, with brand name GYNOPROGEST, 2mg pills daily for 3 months (20 cases) (*Ichigo et al., 2011*)
  - Group (B): women will receive NAC, with brand name GEMACYSTINE, orally at a dose of 600 mg/day for 3 months ( 20 cases) (*Aghaamoo et al., 2021*)
4. **Methodology:** All cases will be subjected to:
  - **Full history taking:** with special emphasis to age, parity, BMI, age of menarche, obstetric history, drug history as well as presence of any medical disease.
  - **Full general examination:** for pallor, fatigue.
  - **Abdominal examination:** to assess the leiomyoma size, surface, contour and consistency.
  - **Bimanual vaginal examination(for uterus <12 weeks):** to confirm its uterine origin.
  - **Vaginal Ultrasound examination with the addition of a transabdominal approach if needed** to diagnose and assess the leiomyoma (size and number).

Ultrasound will be done using the same machine.

The principal investigator will hold regular meetings with the research team to assess data and adverse events.

Serious adverse events will be reported to the research ethics committee, Faculty of medicine, Ain Shams university within 24 hours.

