### **Outcomes:**

- **Primary outcome:**

**Leiomyoma volume:** Size of myoma will be measured at three diameters of myomas (transverse, vertical and anterior-posterior). These measurements will be repeated after 3 months of therapy by the same sonographer.

- **Secondary outcomes:**

- **Dysmenorrhea:** according to the visual analog scale (VAS) is a validated, subjective measure for acute and chronic pain. The scale is composed of 0 (no pain at all) to 10 (worst imaginable pain).

- **Heavy menstrual bleeding (HMB).**

**1. Actual blood loss per menstrual period:** according to PBAC score is seen in Figure 1, also defined by FIGO System is seen in Figure 2 according to frequency, duration, regularity and flow volume.

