**Table 7: Comparison between two groups regarding volume of leiomyoma before and after treatment (largest lesion):**

[figure not shown]
	Group A (Dienogest) (N=20)			Group B (NAC) (N=20)			Z*	P value
	Range	Median	IQR	Range	Median	IQR		
Leiomyoma volume (cm  ) before	1.43-45.24	15.53	4.31-25.01	1.00-108.00	9.00	4.09-14.32	0.52	0.61

Leiomyoma volume (cm  ) after	2.66-76.36	19.54	8.25-32.61	3.24-115.90	13.13	7.74-24.16	0.50	0.63
---	------------	-------	------------	-------------	-------	------------	------	------

\*Mann Whitney U test

Median leiomyoma volume slightly increases after treatment in both groups, but the differences between the groups are not statistically significant ( $p > 0.05$ ), indicating that both treatments had similar effects on leiomyoma volume.

[figure not shown]

[figure not shown]

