**Comparison of outcome measures before and after treatment:**

**Table 11: Comparison between outcome measures before and after treatment in group A (Dienogest):**

	Mean	SD	t*	P value
VAS score for dysmenorrhea before	7.10	2.88	7.74	0.00
VAS score for dysmenorrhea after	1.35	2.35		
Hemoglobin level before	10.54	1.65	2.78	0.01
Hemoglobin level after	10.99	1.41		
	Median	IQR	Z**	P value
Leiomyoma volume (cm3) before	15.53	4.31-25.01	2.78	0.01
Leiomyoma volume (cm3) after	19.54	8.25-32.61		
HMB assessment (PBAC) before	70.00	15.00-110.00	2.88	0.004
HMB assessment (PBAC) after	0.00	0.00-8.50		

\*Paired-samples t test    \*\* Wilcoxon Signed Ranks Test

Significant improvements are observed in VAS scores, HMB assessment, and hemoglobin levels after treatment, suggesting that Dienogest is effective. But leiomyoma volume is significantly increased after treatment.

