**Table 12: Comparison between outcome measures before and after treatment in group B (NAC):**

	Mean	SD	t*	P value
VAS score for dysmenorrhea before	7.30	1.78	6.49	0.00
VAS score for dysmenorrhea after	3.70	1.69		
Hemoglobin level before	11.39	1.46	1.40	0.18
Hemoglobin level after	11.63	1.51		
	Median	IQR	Z**	P value
Leiomyoma volume (cm3) before	9.00	4.09-14.32	3.46	0.001
Leiomyoma volume (cm3) after	13.13	7.74-24.16		
HMB assessment (PBAC) before	50.00	15.00-90.00	1.78	0.08
HMB assessment (PBAC) after	25.00	15.00-70.00		

\*Paired-samples t test    \*\* Wilcoxon Signed Ranks Test

Similar to Group A, Group B also shows significant improvements in VAS scores and increase in leiomyoma volume, though the changes in hemoglobin levels and HMB assessments are less pronounced.

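### SAP Table 7 treats a non-significant test of the primary outcome as evidence that the two treatments act alike

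*SAP*

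**What the plan says.** The protocol (Aim / Objectives) hypothesises that NAC is "more feasible and effective in the reduction of leiomyoma volume with no hormonal side effects compared with Dienogest". Under Outcomes, the primary outcome is leiomyoma volume, from three diameters: "These measurements will be repeated after 3 months of therapy by the same sonographer". Allocation is 1:1 by a computer-generated sequence (Study procedures and interventions). The sample size rests on change: "Assuming an effect size of 1.0 reflecting the percentage change (reduction) in the volume of uterine leiomyoma", with alpha 0.01 and power 0.90; 20 women per group were planned.

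SAP Table 7 gives the following volumes of the largest lesion, as median (IQR) in cm³:

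| | Dienogest (n = 20) | NAC (n = 20) | Z | P |
|---|---|---|---|---|
| Before | 15.53 (4.31–25.01) | 9.00 (4.09–14.32) | 0.52 | 0.61 |
| After | 19.54 (8.25–32.61) | 13.13 (7.74–24.16) | 0.50 | 0.63 |

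The text below the table notes a slight rise in the median in both groups, says that "the differences between the groups are not statistically significant", and concludes from this: "indicating that both treatments had similar effects on leiomyoma volume".

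Tables 11 and 12 test change in volume within each arm only. For dienogest: "But leiomyoma volume is significantly increased after treatment" (Wilcoxon Z = 2.78, P = 0.01). For NAC the text reports "significant improvements in VAS scores and increase in leiomyoma volume" (volume: Z = 3.46, P = 0.001).

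**The concern.** Failure to reject a null hypothesis of no difference is not evidence of no difference. A claim of similarity needs a margin fixed in advance, or at least an interval narrow enough to exclude differences that would matter. Neither is visible here, and equivalence was not a design aim.

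The two tests behind the sentence also differ in what they can say. The baseline test carries no information about treatment effect. The 3-month test is a legitimate unadjusted randomised comparison, but it ignores baseline volume. Change, on which the trial was sized, is never compared between arms; two within-arm P values do not make that comparison.

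This is the SAP's between-group conclusion on the primary outcome. A reader could take NAC as shown to match dienogest on fibroid volume, which the trial has not shown.

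**Working it through.** **Inputs.** n = 20 per arm, and the Z values and quartiles from Table 7; alpha 0.01 from the protocol's sample size justification. Two-sided tests are assumed, since sidedness is not stated.

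**1. The printed P values.** The normal approximation gives P = 0.603 for Z = 0.52 (printed 0.61) and P = 0.617 for Z = 0.50 (printed 0.63). The gaps are small and both results stay clearly non-significant.

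**2. What the 3-month test says about the difference.** Let θ be the probability that a woman in one arm has a larger 3-month volume than a woman in the other. The direction is not printed.

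- SE(θ) = √(400 × 41 / 12) / 400 = 0.0924. This is the null standard error without tie correction, so the intervals are approximate.
- θ = 0.5 + 0.50 × 0.0924 = 0.546
- 95% CI: 0.546 ± 1.96 × 0.0924 = 0.365 to 0.727
- 99% CI: 0.546 ± 2.576 × 0.0924 = 0.308 to 0.784
- θ needed for significance: 0.5 + 1.96 × 0.0924 = 0.681 at 0.05; 0.5 + 2.576 × 0.0924 = 0.738 at 0.01

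**3. The difference the test could have found.** Assume log-normal volumes, with log-SD = ln(Q3/Q1)/1.349.

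- After treatment: dienogest ln(32.61/8.25)/1.349 = 1.019; NAC ln(24.16/7.74)/1.349 = 0.844
- Pooled: √((1.019² + 0.844²)/2) = 0.935
- Ratio detectable with 80% power at 0.05, taking Mann-Whitney efficiency as 0.955: exp(2.80 × 0.935 × √(2/20) / √0.955) = 2.3. At alpha 0.01 it is 2.8.
- Simulated Mann-Whitney power at 0.05: about 0.25 for a ratio of 1.5 and 0.60 for a ratio of 2.0.

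So if one arm's volumes had truly been 50% larger, the test would have missed it about three times in four.

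**4. Change between arms.** Ratio of medians, after to before: NAC 13.13/9.00 = 1.459; dienogest 19.54/15.53 = 1.258. Their quotient is 1.459/1.258 = 1.16. Its interval needs patient-level data.

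**5. Illustration of a baseline-adjusted analysis.** Take the log difference after treatment minus b times the log difference before, where b is the pooled slope implied by an assumed before-after correlation r. Baseline log-SDs are 1.303 (dienogest) and 0.929 (NAC); intervals use t with 37 df. NAC/dienogest ratios (95% CI):

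| r | b | Centres from medians | Centres from quartile midpoints (log scale) |
|---|---|---|---|
| 0.80 | 0.659 | 0.96 (0.66–1.40) | 1.02 (0.70–1.48) |
| 0.90 | 0.742 | 1.01 (0.76–1.33) | 1.05 (0.80–1.37) |
| 0.98 | 0.808 | 1.04 (0.91–1.19) | 1.07 (0.94–1.21) |

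The printed within-arm Wilcoxon Z values (2.78 and 3.46) give a rough check on r. With quartile midpoints, the expected values are about 2.3 and 3.3 at r = 0.8, 2.8 and 3.7 at r = 0.9, and 3.6 and 3.9 at r = 0.98. The first two fit better than the last. At r = 0.8 to 0.9 the intervals run from volumes 20% to 34% smaller on NAC to volumes 33% to 48% larger.

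**The case against.** The strongest reply is that the fault lies in one clause. The same sentence admits that volume rose in both arms, Tables 11 and 12 say so again, and Table 7 prints medians, IQRs, Z and P for the reader to judge. The SAP does not claim formal equivalence, non-inferiority or superiority of NAC, and its dysmenorrhea and PBAC conclusions do not depend on this clause. On a loose reading, *similar* means only that both arms moved the same way.

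The loose reading does not hold, because the sentence draws the conclusion from P > 0.05. A shared direction also puts no bound on the difference between arms. Table 10 shows the SAP can be more careful: for hemoglobin it reports a non-significant between-group difference and stops there.

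Some of the reply does stand. The test itself is not wrong; the interpretation is. The baseline-adjusted figures rest on assumed correlations and log-normality, and they allow smaller as well as larger volumes on NAC. A Hodges-Lehmann shift or a rank probability with its interval would also be an acceptable estimate. Finally, the figures under Table 7 were not available, so the remark about missing estimates is confined to the visible text and tables.

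**Conclusion.** The concern holds, and the sentence must change because it is the conclusion on the primary outcome. Table 7 shows that no significant difference in 3-month volume was detected and that superiority of NAC was not demonstrated. It does not show similar effects: the approximate 95% CI for the rank probability is 0.37 to 0.73, and only a volume ratio of about 2.3 had 80% power at 0.05.

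The rank interval rests on the printed Z, 20 per arm and the null standard error. The power figures add log-normality with the printed IQRs, and the baseline-adjusted ratios add an assumed correlation. The verdict needs none of these reconstructions. It follows from the inference as written, the superiority hypothesis, and the absence of a margin, estimate or interval in the visible documents. Nor do the calculations show that the treatments differ.

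**What to change.** 1. In the text under Table 7, keep the remark that median volume rose in both groups and replace the conclusion with wording such as: *No statistically significant difference in leiomyoma volume at 3 months was detected; superiority of NAC was not shown, and the trial set no equivalence margin and does not establish similar effects.*

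2. Add one between-group estimate from the paired volumes: log 3-month volume regressed on treatment and log baseline volume, reported as a NAC/dienogest ratio with a 95% CI. Label it as added after the results were seen, and check the log-scale assumption. If that assumption fails, report a Hodges-Lehmann shift or a rank probability with its interval. Word any statement about relative change according to that result.

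The cost is one sentence and one analysis, with no new data. The stated conclusion becomes less favourable.

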**Table 8: Comparison between two groups regarding dysmenorrhea VAS score before and after treatment:**

	Group A (Dienogest) (N=20)			Group B (NAC) (N=20)			t*	P value
	Range	Mean	SD	Range	Mean	SD		
VAS score for dysmenorrhea before	2.00-10.00	7.10	2.88	5.00-10.00	7.30	1.78	0.26	0.79
VAS score for dysmenorrhea after	.00-8.00	1.35	2.35	1.00-7.00	3.70	1.69	3.64	0.001

\*Student t test

A significant reduction in VAS scores for dysmenorrhea is observed in both groups after treatment, with Group A showing a more pronounced improvement ( $p = 0.001$ ).

[figure not shown]

[figure not shown]
**Table 9: Comparison between two groups regarding HMB assessment before and after treatment:**

	Group A (Dienogest) (N=20)			Group B (NAC) (N=20)			Z*	P value
	Range	Median	IQR	Range	Median	IQR		
HMB assessment (PBAC) before	10.00-200.00	70.00	15.00-110.00	10.00-200.00	50.00	15.00-90.00	0.9	0.86
HMB assessment (PBAC) after	.00-200.00	.00	.00-9.00	3.00-200.00	25.00	15.00-70.00	4.10	0.00

\*Mann Whitney U test

Group A shows a significant reduction in PBAC scores after treatment, indicating a better response to treatment compared to Group B (P value = 0.00).

[figure not shown]

[figure not shown]

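### SAP Table 9: the baseline PBAC row prints Z = 0.9 with P = 0.86, which do not belong together (a minor reporting error), and the claim of better response should be tested with baseline PBAC adjusted for

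*SAP*

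**What the plan says.** The protocol lists menstrual blood loss by PBAC score among the secondary outcomes. SAP Table 9 compares it between arms of 20 women each, before and after treatment, and its footnote names the "Mann Whitney U test". The row at issue is the one labelled "HMB assessment (PBAC) before". The two rows, in the order group A range, median and IQR, group B range, median and IQR, Z and P, are:

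- "HMB assessment (PBAC) before 10.00-200.00 70.00 15.00-110.00 10.00-200.00 50.00 15.00-90.00 0.9 0.86"
- "HMB assessment (PBAC) after .00-200.00 .00 .00-9.00 3.00-200.00 25.00 15.00-70.00 4.10 0.00"

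The only sentence of interpretation is: "Group A shows a significant reduction in PBAC scores after treatment, indicating a better response to treatment compared to Group B (P value = 0.00"). It says nothing about the baseline row.

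Table 11 repeats the group A PBAC summaries for the within-group test. The medians and the baseline quartiles agree with Table 9, but the post-treatment upper quartile is 8.50 there, not 9.00.

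**The concern.** A Mann-Whitney Z and its P value are two forms of one result, so a reader can convert one into the other. In the baseline PBAC row the conversion fails by a wide margin, and at least one of the two figures must be wrong. The quartile mismatch adds a second small fault to the same outcome.

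PBAC has the largest between-arm test statistic of the outcomes in Tables 7 to 10, so its table should be free of visible errors. A related weakness lies in the wording under the table. It speaks of a reduction and of better response relative to group B, but the P value it cites compares post-treatment levels only. How far such a comparison speaks to response depends on where the arms started, and the printed baseline medians are 70 and 50.

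**Working it through.** **Inputs.** Table 9: baseline Z = 0.9, P = 0.86; post-treatment Z = 4.10, P = 0.00; 20 women per arm. Table 7, same test: baseline volume "1.43-45.24 15.53 4.31-25.01 1.00-108.00 9.00 4.09-14.32 0.52 0.61", so Z = 0.52 and P = 0.61; volume after treatment Z = 0.50, P = 0.63. Sidedness is not stated. Two-sided is assumed, because the other rows fit it.

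**Formula.** Two-sided P = 2 × (1 − Φ(|Z|)).

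**Does the formula fit the other Mann-Whitney rows?**

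| Row | Z | Computed P | Printed P |
|---|---|---|---|
| Volume before (Table 7) | 0.52 | 0.603 | 0.61 |
| Volume after (Table 7) | 0.50 | 0.617 | 0.63 |
| PBAC after (Table 9) | 4.10 | 0.00004 | 0.00 |
| PBAC before (Table 9) | 0.9 | 0.368 | 0.86 |

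The first three agree to within about 0.01. The baseline PBAC row is the outlier.

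**Can any standard variant turn Z = 0.9 into P = 0.86?**

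- Z anywhere from 0.85 to 0.95 (rounding): P from 0.40 to 0.34.
- One-sided: 0.184. Lower tail Φ(0.9): 0.816.
- t distribution with 38 df: 0.374.
- Exact null distribution for 20 versus 20, no ties, at U = 166 and 167 (Z = 0.92 and 0.893): 0.369 and 0.383. With a continuity correction: 0.365 and 0.379.
- Misplaced decimal, Z = 0.09: 0.928.

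None gives 0.86.

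**What Z does P = 0.86 need?**

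- Normal approximation: Z = Φ⁻¹(1 − 0.86/2) = 0.176; over P from 0.855 to 0.865, Z runs from 0.183 to 0.170.
- Exact test: the SD of U is √(20 × 20 × 41 / 12) = 36.97. At U = 193, Z = (200 − 193)/36.97 = 0.189 and exact P = 0.862.

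A Z of 0.19 with P = 0.86 is therefore a coherent pair, and 0.9 is what remains of 0.19 if the 1 is dropped. It is also the only Z or t in Tables 7 to 10 printed to one decimal.

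**Can the printed summaries decide between them?** No. Artificial data filled in to match the printed medians, quartiles and ranges gave Z mostly between about 0.2 and 0.9 (5th to 95th percentile). That rests on an assumption about how the unseen scores spread between the quartiles.

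**The quartile.** One dataset can yield both values. As an illustration, with n = 20 suppose the 15th and 16th ordered scores are 8 and 10. Linear interpolation at position 1 + 0.75 × 19 = 15.25 gives 8 + 0.25 × 2 = 8.50. The median of the upper half gives (8 + 10)/2 = 9.00. Rounding 8.5 up to 9 would do the same.

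**The response claim.** Group A moves from a median of 70 to 0, group B from 50 to 25. The differences between medians are 70 and 25 (not the same as median changes, which are not printed). No table compares change, or baseline-adjusted PBAC, between the arms. Tables 11 and 12 test each arm separately (P = 0.004 and 0.08), which is not a between-arm test.

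**The case against.** The strongest case on the other side is that this is one missing character. If Z was 0.19, then P = 0.86 is correct and nothing of substance is misreported. The Table 7 P values run slightly above the normal approximation, as exact P values would, which makes this reading more plausible. It is not proven, and only the data can settle it.

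A reader might go further and infer that the baseline comparability behind the bleeding result is misstated. The documents do not support that. No sentence in the SAP claims that PBAC was balanced at baseline, neither the post-treatment test nor the within-group tests use the baseline P value, and both candidate P values are non-significant. In any case a large baseline P with 20 women per arm does not establish similarity. The medians and IQRs are printed for the reader to judge.

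A reader might also infer from 9.00 and 8.50 that the PBAC rows came from inconsistent runs. That does not follow either: rounding or a second quartile method explains the gap, and every other PBAC median and quartile agrees between Table 9 and Tables 11 and 12.

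Finally, the misprint creates no need for an adjusted analysis. That is right, and the adjusted analysis is recommended on a separate ground: the text claims a difference in response that the cited test does not directly address.

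**Conclusion.** Z = 0.9 and P = 0.86 are incompatible, so at least one is wrong. This holds under every standard version of the test that was tried. Which figure is wrong cannot be determined from the documents: the true P is about 0.37 if Z is right, or 0.86 if P is right, with a lost digit in Z a plausible cause. The quartile disagreement is real at the printed precision and probably benign. Both are minor reporting errors that change no conclusion.

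The separate point on the response claim is also modest. Group A started with the higher median and finished with the lower, so if baseline and post-treatment scores are positively related, adjustment is unlikely to reverse the direction of the post-treatment result (Z = 4.10). It would, however, put the stated claim on a test that matches it.

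**What to change.** - Recheck the baseline PBAC row of Table 9 against the data and print the Z and P that belong together, stating whether P is exact or asymptotic.
- Give one value for group A's post-treatment upper quartile in Tables 9 and 11, with one quartile method and one rounding rule.
- Add a between-arm comparison of post-treatment PBAC with baseline PBAC as a covariate, by rank-based analysis of covariance, with midranks for the many tied zeros in group A. Base the sentence on better response on that result, or else limit it to post-treatment levels.

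The cost is a rerun of one table and one extra model on data already collected. Because the results have been seen, the adjusted comparison should be labelled as added afterwards.

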**Table 10: Comparison between two groups regarding hemoglobin level before and after treatment:**

	Group A (Dienogest) (N=20)			Group B (NAC) (N=20)			t*	P value
	Range	Mean	SD	Range	Mean	SD		
Hemoglobin level before	7.60-12.80	10.54	1.65	9.30-13.60	11.39	1.46	1.73	0.09
Hemoglobin level after	8.20-13.20	10.99	1.41	7.90-13.80	11.63	1.51	1.39	0.17

\*Student t test

While hemoglobin levels increase slightly in both groups after treatment, the differences between the groups are not statistically significant ( $p > 0.05$ ).

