### **Sample Size:**

The study will be conducted on 40 women; they will be subdivided into 2 equal groups.

Group (A): women will receive Dienogest, with brand name GYNOPROGEST, 2mg pills daily for 3 months (20 cases) (*Ichigo et al., 2011*)

Group (B): women will receive NAC, with brand name GEMACYSTINE, orally at a dose of 600 mg/day for 3 months ( 20 cases) (*Aghaamoo et al., 2021*)

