**2. using the measurement of hemoglobin.**

Pads		
1 point	For each lightly stained pad	
5 points	For each moderately stained pad	
20 points	For each completely saturated pad	
Tampons		
1 point	For each lightly stained tampon	
5 points	For each moderately stained tampon	
10 points	For each completely saturated tampon	
Clots/Flooding		
1 point	For each small clot	
5 points	For each large clot	
5 points	For each episode of flooding	

  

Parameter	Normal	Abnormal	
Frequency	Absent (no bleeding) = amenorrhea		
	Infrequent (>38 days)		
	Normal (≥24 to ≤38 days)		
	Frequent (<24 days)		
Duration	Normal (≤8 days)		
	Prolonged (>8 days)		
Regularity	Normal or "Regular" (shortest to longest cycle variation: ≤7-9 days)*		
	Irregular (shortest to longest cycle variation: ≥8-10 days)*		
Flow Volume (patient determined)	Light		
	Normal		
	Heavy		
Intermenstrual Bleeding (IMB) Bleeding between cyclically regular onset of menses	None		
	Random		
	Cyclic (Predictable)	Early Cycle	
		Mid Cycle	
		Late Cycle	
Unscheduled Bleeding on Progestin ± Estrogen  Gonadal Steroids (birth control pills, rings, patches or injections)	Not Applicable (not on gonadal steroid medication)		
	None (on gonadal steroid medication)		
	Present		

**FIGURE 2** The FIGO AUB System (*Munro et al., 2018*)

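### Table 10 compares raw 3-month hemoglobin between arms that started 0.85 apart; adjusting for baseline moves the estimate to near zero and halves its interval, and the result stays non-significant

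*SAP*

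**What the plan says.** The protocol's Outcomes section lists hemoglobin as the second way of assessing heavy menstrual bleeding, a secondary outcome: "using the measurement of hemoglobin". On size, the protocol states "The study will be conducted on 40 women; they will be subdivided into 2 equal groups".

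SAP Table 10 compares the arms twice, with the footnoted method "Student t test". Its rows give range, mean and SD for dienogest, then the same for NAC, then t and P:

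- "Hemoglobin level before 7.60-12.80 10.54 1.65 9.30-13.60 11.39 1.46 1.73 0.09"
- "Hemoglobin level after 8.20-13.20 10.99 1.41 7.90-13.80 11.63 1.51 1.39 0.17"

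The text below the table concludes: "While hemoglobin levels increase slightly in both groups after treatment, the differences between the groups are not statistically significant".

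Tables 11 and 12 add paired tests within each arm. The dienogest row is "Hemoglobin level before 10.54 1.65 2.78 0.01" and the NAC row is "Hemoglobin level before 11.39 1.46 1.40 0.18" (mean, SD, paired t, P). The available SAP text contains no between-arm comparison of change and no baseline-adjusted comparison.

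**The concern.** A woman's hemoglobin at 3 months depends heavily on where she started. If the arms start apart, a t test on final values mixes that starting gap with any treatment effect. It also leaves in the error term all the between-woman variation that the baseline value would explain.

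Here the starting gap (-0.85) is larger than the final gap (-0.64), so the sign of the tested difference may come from the starting levels alone. At stake are the size and precision of the only between-arm hemoglobin estimate. As tabulated, the data look compatible with a NAC advantage of nearly 1.6 g/dL.

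**Working it through.** All differences are dienogest minus NAC, with n = 20 per arm. The SAP prints no unit for hemoglobin; g/dL is assumed.

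**Inputs.** Table 10 gives before 10.54 (SD 1.65) and 11.39 (SD 1.46), and after 10.99 (SD 1.41) and 11.63 (SD 1.51). Tables 11 and 12 give paired t 2.78 and 1.40.

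**1. Reproduce Table 10** (pooled SD, 38 df).
- Before: difference -0.85; SE = 1.558 × √(2/20) = 0.493; |t| = 1.73, P = 0.09. Matches.
- After: difference -0.64; SE = 1.461 × √(2/20) = 0.462; |t| = 1.39, P = 0.17. Matches. The 95% CI, not printed in the SAP, is -1.58 to 0.30, width 1.87.

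**2. SD of change** = (mean change / paired t) × √20.
- Dienogest: 0.45 / 2.78 × 4.472 = 0.724.
- NAC: 0.24 / 1.40 × 4.472 = 0.767.
- The paired t values on 19 df give P = 0.012 and 0.178, agreeing with the printed 0.01 and 0.18. This supports all 20 women per arm being included.

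**3. Before-after correlation** r = (SD_before² + SD_after² − SD_change²) / (2 × SD_before × SD_after).
- Dienogest: r = 0.90.
- NAC: r = 0.87.

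**4. Analysis of covariance** (3-month value on arm and baseline, common slope, 37 df).
- Within-arm sums: Sxx = 19 × (1.65² + 1.46²) = 92.2; Syy = 19 × (1.41² + 1.51²) = 81.1; Sxy = 19 × (0.900 × 1.65 × 1.41 + 0.867 × 1.46 × 1.51) = 76.1.
- Slope = 76.1 / 92.2 = 0.825.
- Residual SD = √[(81.1 − 76.1²/92.2) / 37] = 0.703.
- Final gap predicted by the starting gap alone: 0.825 × (-0.85) = -0.70.
- Adjusted difference = -0.64 − (-0.70) = +0.06.
- SE = 0.703 × √(2/20 + 0.85²/92.2) = 0.231.
- 95% CI -0.41 to 0.53, P = 0.79, width 0.94.
- Width ratio 0.94 / 1.87 = 0.50. Variance ratio (0.462 / 0.231)² = 4.0, equivalent to about four times the sample size for this outcome.

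**5. Sensitivity.** Varying every printed input within ±0.005 keeps the adjusted difference between +0.04 and +0.08 and the width ratio between 0.48 and 0.52. Separate slopes (0.77 and 0.90) give +0.07 at the midpoint of the baseline means.

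**6. Change scores.** The difference in change is 0.45 − 0.24 = +0.21, SE = √[(0.724² + 0.767²)/20] = 0.236, 95% CI -0.27 to 0.69, P = 0.38.

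**7. Other outcomes.** For the dysmenorrhea VAS, steps 2 and 3 give SDs of change of 5.75 / 7.74 × 4.472 = 3.32 and 3.60 / 6.49 × 4.472 = 2.48, and correlations of about 0.2 and 0.0. Adjustment would matter little there. Leiomyoma volume and PBAC are printed as medians, interquartile ranges and rank-test Z values, which do not yield a before-after correlation.

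**The case against.** **The conclusion does not change.** Correct. P moves from 0.17 to 0.79, and the SAP never claims a hemoglobin advantage for NAC; it reads the result as null. What remains is that the implied estimate and its uncertainty are poor. The limit on a NAC advantage falls from about 1.6 to about 0.4 g/dL.

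**The starting gap is visible, and Tables 11 and 12 show the changes.** True, nothing is hidden. But one within-arm P of 0.01 beside another of 0.18 is not a comparison of the arms. A reader might infer that dienogest raised hemoglobin more than NAC did. The documents do not support that: the larger raw gain (0.45 against 0.24) is descriptive, the difference in change has P = 0.38, and the adjusted difference is close to zero.

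**The baseline gap has P = 0.09, so it may be chance.** It may. The case for adjustment rests on correlations near 0.9, not on a baseline significance test.

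**Choosing a model after seeing the results, for one outcome, is selective.** This stands. It is why the analysis should be labelled post hoc and the same rule applied to all continuous outcomes.

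**Summaries cannot show influential values.** This also stands. The NAC minimum fell from 9.30 to 7.90, so with the same women at both times at least one fell by 1.40 or more. That is (1.40 + 0.24) / 0.767 = 2.1 SDs of change from the arm mean. Her effect on the slope and residual SD needs the individual data.

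**Conclusion.** The point holds as an inefficient and poorly centred estimate for a secondary outcome, not as a wrong verdict. The raw difference of -0.64 is about what the starting gap alone predicts (-0.70). Adjusted for baseline it is about +0.06 (SE 0.23, 95% CI -0.41 to 0.53), with an interval half as wide.

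The rebuilt figures assume a common slope, all 20 women per arm in the paired tests, and no unduly influential values. The correlations are derived rather than printed. The SAP's opening pages were not available, so any methods text there is unchecked; Table 10's own footnote names the test used.

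A reader might also infer that only hemoglobin is affected. The documents do not support that. The VAS can be checked and is little affected, but Tables 7 and 9 also compare raw final values for leiomyoma volume and PBAC. For volume, the primary outcome, the baseline medians were 15.53 and 9.00 cm³. Whether adjustment would matter for these two cannot be judged from what is printed.

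**What to change.** - In Table 10, replace the post-treatment t test with an analysis of covariance of 3-month hemoglobin on arm and baseline hemoglobin. Label it post hoc and report the adjusted difference with its 95% CI. Keep the raw means as description.
- Reword the text to say that no between-arm hemoglobin difference was detected after allowing for the lower starting level on dienogest, and give the interval from the individual data.
- Check residuals and influence, in particular the woman or women with a large fall on NAC.
- State one baseline-adjustment rule for all continuous outcomes, including leiomyoma volume and PBAC, using a suitable scale such as logs or ranks for the skewed ones. PBAC includes zeros after treatment, so a plain log will not serve there.

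The cost is one regression per continuous outcome on data already collected, and a few sentences of SAP text.
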